1.0 PROTOCOL SYNOPSIS

Study Title:	A Prospective, Non-Randomized Study to Evaluate Treatment Outcome of Nasal Airway Obstruction Using the Aerin Medical Vivaer™ Stylus
Study Device:	Aerin Medical Vivaer Stylus
Device Description:	The Vivaer Stylus is a disposable handheld device capable of delivering bipolar radiofrequency energy to tissue.
Proposed Indication:	The Vivaer Stylus is indicated for the treatment of nasal obstruction by the modification of submucosal tissue including cartilage in the internal nasal valve area.
Study Objective:	The main objective of this research is to evaluate the outcome of treating nasal airway obstruction with the Aerin Medical Vivaer Stylus
Study Design:	Prospective, non-randomized study to evaluate treatment outcome of nasal airway obstruction using the Aerin Medical Vivaer stylus
Subject Population:	Male and female subjects who present with symptoms associated with chronic nasal obstruction
Study Procedures:	Subjects will have both nasal valves treated in a single treatment session. Follow-Up and Study Exit will be at 90 Days, Post-Procedure. No repeat ("touch-up") procedures will be permitted during the 90 day follow-up period.
Study Endpoints:	
Primary Endpoint variable(s) – The primary symptom outcome variables include self-reported Nasal Obstruction Symptoms Evaluation (NOSE) score and Visual Analog Scale (VAS) of nasal obstruction. One-way ANOVA with repeated measures will be used to compare post-treatment vs. baseline measurements and determine the effectiveness of the treatment.
 
The primary independent endpoint variables include several categories: 1) variables that index general disease severity (Computerized Tomography (CT) staging and endoscopic examination score 2) peak inspiratory flow measurements of nasal physical resistance.
 
Secondary outcome variables will include age, gender, race, duration of the disease, and medical and smoking histories. The potential confounding effect of the secondary outcome variables will be examined.

Study Evaluations:	
1. Nasal Obstruction Symptoms Evaluation (NOSE) score2. Visual Analog Scale (VAS) of nasal obstruction

3. Endoscopic examination (video and pictures), Lund-Kennedy endoscopic scores
4. Peak nasal inspiratory flow
5. Cone beam CT scan (clinical or research)
6. Sino-Nasal Outcome Test (SNOT-22)
7. Computational modeling of nasal airflow based on CT scan of each visit.

Study Size: Up to 20 patients meeting the inclusion/exclusion criteria will be recruited.

Anticipated Duration: Enrollment completion/Q2 2019; Follow-Up completion/Q3 2019

Study Visits: Phase 1 - Pre-Admission Evaluation/Patient Consent

Phase 2 – Baseline/Treatment

Phase 3 – Follow-Up 90 Days Post-Procedure / Study Exit

Study Eligibility Criteria:

Inclusion Criteria:

Eligible subjects will meet all the following:

1. Age 18 to 75 years (inclusively)
2. Willing and able to provide informed consent
3. Willing and able to comply with the subject-specific requirements outlined in the study protocol
4. Complaints of nasal obstruction for at least 1 year
5. Failed maximum medical therapy (4-6 weeks of steroids)
6. Nasal Obstruction Symptom Evaluation (NOSE) score of ≥ 60 at Baseline
7. Nasal valve is a primary or significant contributor to the subject's nasal obstruction as determined by the study investigator (based on clinical presentation, physical examination, nasal endoscopy, etc.) and the subject has a positive response to any of the following temporary measures (based on patient history or during office exam):
 - a. Use of external nasal dilator strips (e.g., Breathe Right Strips)
 - b. Q-Tip test (manual intranasal lateralization)
 - c. Use of nasal stents
 - d. Cottle Maneuver (manual lateral retraction of the cheek)

Exclusion Criteria:

Subjects will not be enrolled if they meet any of the following:

1. Prior surgical treatment of the nasal valve
2. Rhinoplasty, septoplasty, inferior turbinate reduction or other surgical nasal procedures within the past three (3) months
3. Severe and/or chronic sinusitis, recurrent sinusitis, or allergies leading to nasal obstruction and currently requiring oral corticosteroid therapy
4. Severe case of any of the following: septal deviation, turbinate hypertrophy, polyps, or ptotic nose tip believed to be the primary contributor to the subject's nasal obstruction symptoms and warranting surgical intervention
5. Known or suspected allergies or contraindications to the anesthetic agents and/or antibiotic medications to be used during the study procedure session
6. Known or suspected to be pregnant, or is lactating
7. Other medical conditions which in the opinion of the investigator could predispose the subject to poor wound healing or increased surgical risk.

2.0 OVERALL OBJECTIVES

The study will evaluate the outcome of nasal obstruction treated with the Vivaer™ Stylus, and also attempt to use computational aerodynamics simulation and sensory measurements to identify and predict patients' treatment outcome. The ability to envisage variables that will lead to best outcome may have potential to assist patients and clinicians in planning effective, well-informed, personalized treatment/surgery strategies.

2.1 Primary outcome variables

The primary symptom outcome variables include self-reported Nasal Obstruction Symptoms Evaluation (NOSE) score and VAS of nasal obstruction.

The primary independent objective variables include several categories: 1) variables that index general disease severity (Computerized Tomography (CT) staging and endoscopic examination score), 2) peak inspiratory flow measurements of nasal physical resistance.

2.2 Secondary outcome variables

Secondary outcome variables will include age, gender, race, duration of the disease, and medical and smoking histories. The potential confounding effect of the secondary outcome variables will be examined.

3.0 BACKGROUND AND RATIONALE

The nasal valve area (V) represents the narrowest segment of the nasal airway. It is defined as the area bounded by the caudal end of the upper lateral cartilage (ULC), cartilaginous nasal septum (S) and head of the inferior turbinate (T) (Figure 1). The nasal valve angle is the angle between the upper lateral cartilage and the nasal septum. Anatomical studies have shown that this angle classically ranges between 10° and 15° in the nose of Caucasian individuals. The nasal valve is a critical site for nasal resistance and for nasal obstruction symptoms. One of the most common causes of nasal obstruction is internal nasal valve dysfunction wherein the upper lateral cartilage moves towards the septum, increasing airway resistance and leading to nasal obstruction.

[figure not shown]

Figure 1. Nasal Anatomy
(from Weaver 2012¹, Figure 1)

Airway remodeling in the nasal valve region may have significant benefit for patients with a narrow nasal valve. Over-the-counter remedies such as external breathing strips can provide patients with temporary relief. However, a long-term solution to chronic nasal airway obstruction associated with the nasal valve usually involves extensive surgery. One of the common surgical procedures targeting the nasal valve is the implantation of alar batten grafts; i.e., curved cartilage supports placed into areas of the nasal valve area to enlarge and strengthen it. Although batten graft surgical outcomes are generally successful, the procedure requires the harvesting of a cartilage graft from another anatomic site, a difficult and time-consuming procedure. Overall, current surgical therapy on the nasal valve is efficacious, but is invasive and associated with long recovery periods and the risk of complications, e.g., hemorrhage.

The use of radiofrequency energy has been common for decades in the fields of otolaryngology, neurosurgery, cardiology, urology and general surgery. For instance, radiofrequency turbinate reduction (RFTR) uses radiofrequency to create heat within the submucosal tissue of the turbinate, reducing tissue volume with minimal impact on surrounding tissues. Numerous studies have demonstrated that radiofrequency therapy in the nasal passage can be safe and effective in improving nasal obstruction and in preserving nasal function.^{2,3}

The Aerin Medical Vivaer™ System is an investigational device that is capable of delivering bipolar radiofrequency energy to improve nasal breathing by modifying soft tissues of the nasal valve. The System is comprised of the Vivaer Stylus (Figure 2), a disposable handheld device capable of delivering bipolar radiofrequency energy to tissue, and a radiofrequency generator (Figure 3).

[figure not shown]

Figure 2. Vivaer™ Stylus

The Vivaer™ Stylus consists of a handle, shaft and treatment tip. An array of bipolar electrodes is positioned on a non-conductive tip which is attached to the handle via a non-conductive shaft. A temperature sensor (thermocouple) is located on the tip to monitor tissue temperature. The Stylus is attached to a temperature-controlled radiofrequency generator via a flexible cable. The Vivaer Stylus modifies the soft tissues of the nasal valve through the use of low doses of radiofrequency energy. The low-power radiofrequency generates heat within the submucosal tissue, creating a coagulation lesion. As the lesion heals, the tissue retracts and stiffens, slightly widening the nasal valve area. This decreases the nasal airflow resistance thereby improving inflow of air through the nose (as demonstrated in earlier pre-clinical and pilot studies). The procedure requires local anesthesia only, and is much less invasive than current surgical approaches.

This clinical study plans to use computational fluid dynamics (CFD) and various sensory testing techniques to examine the factors contributing to patients' outcome after Aerin treatment. The efficacy and safety of the Vivaer Stylus treatment will be recorded.

[figure not shown]

Figure 3. Aerin Console

4.0 PROCEDURES

4.1 Research Design

The study will be conducted by the Department of Otolaryngology, The Ohio State University School of Medicine, in conjunction with Aerin Medical. This study is a prospective, case series design, involving a group of patients with chronic nasal obstruction symptoms. The study is a longitudinal design, involving two test sessions: one at baseline (pre-treatment) and one at 90 days post-treatment.

4.2 Study Size

Up to Twenty (20) patients meeting the inclusion/exclusion criteria will be recruited.

4.3 Inclusion Criteria

Eligible subjects will meet all the following:

1. Age 18 to 75 years (inclusively)
2. Willing and able to provide informed consent
3. Willing and able to comply with the subject-specific requirements outlined in the study protocol
4. Complaints of nasal obstruction for at least 1 year
5. Failed maximum medical therapy (4-6 weeks of steroids)
6. Nasal Obstruction Symptom Evaluation (NOSE) score of ≥ 60 at Baseline
7. Nasal valve is a primary or significant contributor to the subject's nasal obstruction as determined by the study investigator (based on clinical presentation, physical examination, nasal endoscopy, etc.) and the subject has a positive response to any of the following temporary measures (based on patient history or during office exam):
 - a. Use of external nasal dilator strips (e.g., Breathe Right Strips)
 - b. Q-Tip test (manual intranasal lateralization)
 - c. Use of nasal stents
 - d. Cottle Maneuver (manual lateral retraction of the cheek; see Figure 4)

[figure not shown]

Figure 4. Cottle Maneuver

Figure 4 demonstrates the Cottle Maneuver as the patient or the physician temporarily lifts and laterizes the skin around the nose and cheek, increasing the nasal valve angle, and potentially increasing nasal airflow. A positive response can be an indicator that the patient will respond well to an increase in nasal valve angle.

The Q-Tip test is another evaluation of potential positive response. A Q-tip is placed gently within the nares against the lateral nasal wall at the location of the narrowest nasal valve region and is pushed outward lightly to expand the nasal valve angle. A positive response to this maneuver may also predict the potential benefit of nasal valve correction.

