For those potential candidates who agree to participate in the study by signing the IRB approved Informed Consent Form (ICF), a baseline evaluation will be conducted. Subjects will be considered enrolled once they arrive at the study clinic to undergo the procedure. At this time a subject identification number will be assigned along with the subject binder.

During the baseline and follow-up visits, the procedures listed below will occur

1. Endoscopic examination (video and pictures), Lund-Kennedy endoscopic scores
2. Peak nasal inspiratory flow
3. Cone beam CT scan (clinical CT at baseline; clinical or research CT at 90-day follow-up visit)
4. Nasal Obstruction Symptom Evaluation (NOSE) scale
5. Sino-Nasal Outcome Test (SNOT-22)
6. Visual analogue scale (VAS) rating severity of nasal obstruction
7. Computational modeling of nasal airflow based on CT scan of each visit.

During the baseline visit, data collection will be performed first, and then the Aerin Vivaer™ Treatment will be provided in the clinic by the physician. The styluses used in this study will be manufactured and supplied by the sponsor.

During the treatment, 0.5 ml of local anesthesia (lidocaine 1% with epinephrine 1:100,000) will be injected into the target tissue. The Vivaer stylus will be inserted into the nose and the electrode-containing tip will be positioned against the target tissue.

Subjects will have both nasal valves treated in a single study procedure session. Each nostril will be treated at up to 3 non-overlapping positions along the upper lateral nasal valve region.

Treatment settings to be used are:

Temperature.....60°C
Power 4 Watts
Treatment Time 18 secs
Cooling Time 12 secs

Accurate positioning will be confirmed by observing the temperature change on the RF generator screen as the stylus tip comes in contact with the target tissue.

No repeat ("touch-up") procedures will be permitted during the 90-day follow-up period.

Immediate Post-Procedure Care (prior to leaving the clinic)

At the discretion of the physician, the following care and instructions may be provided:

- Apply petroleum jelly to the treatment area as needed.

- The patient should be instructed not to manipulate the treatment site for 24 hours with the exception of any necessary hemostasis.

Study subjects will be reminded of their next follow-up visit and will be scheduled within the study window (90 ± 15 days).

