4.9 Data Analysis

Treatment effectiveness

Outcome variables: patient's ratings of nasal obstruction via a VAS and NOSE score as well as the SNOT-22 questionnaire and peak inspiratory flow rate. One-way ANOVA with repeated measures will be used to compare post-treatment vs. baseline measurements and determine the effectiveness of the treatment.

Hypothesis:

Nasal valve region airflow and airflow induced cooling is critical for patients' subjective nasal patency.

Many publications suggest that sensory feedback is as important to perception of nasal obstruction as nasal resistance. For example: Topical or oral application of menthol produces the illusion of decongestion and improved nasal airflow without actually altering nasal resistance¹⁰. Topical application of local anesthetics results in an artificial sensation of nasal obstruction, presumably due to blocking of the trigeminal afferents¹¹.

The Ohio State University (OSU) staff have published a series of studies^{6,12,13} with individualized Computational Fluid Dynamics models and demonstrated that nasal cooling during breathing at the nasal valve region and the nasal trigeminal nerve sensitivity are key to the perception or absence of nasal obstruction. The combination of these variables can predict the subject's ratings (excellent, normal and moderately obstructed) with 89.3% success. It is likely that nasal valve width and shape may have an optimal range in order to achieve both low nasal resistance and high regional mucosal cooling (see Fig. 5). This study will examine a broad list of factors that may contribute to patients' subjective outcomes, not just limited to nasal resistance alone, that include CFD simulation of nasal airflow, mucosa cooling and mucosa sensitivity responding to that cooling.

[figure not shown]

Figure 5. Computational simulation of nasal cooling

- a) high regional cooling, no complaints
- b) low nasal cooling with moderate ratings of nasal obstruction

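### The NOSE score that admits patients appears to double as the analysis baseline, so regression to the mean would inflate the uncontrolled NOSE improvement

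*Combined protocol and SAP*

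**What the plan says.** Inclusion criterion 6, in the synopsis and in section 4.3, requires a "Nasal Obstruction Symptom Evaluation (NOSE) score of ≥ 60 at Baseline". NOSE is one of the two primary symptom outcomes; VAS is the other (section 2.1).

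Four places bear on when the pre-treatment score is taken:

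- Section 4.1 describes a longitudinal design "involving two test sessions: one at baseline (pre-treatment) and one at 90 days post-treatment", that is, one pre-treatment session.
- Table 1 in section 4.7 marks NOSE under Screening/Evaluation and under the 90-day visit, and not under Baseline/Study Procedure. VAS, SNOT-22, peak flow and SF-36 are all marked under Baseline/Study Procedure, so the NOSE row stands out.
- The text of section 4.7 says "During the baseline and follow-up visits, the procedures listed below will occur", and item 4 of that list is the "Nasal Obstruction Symptom Evaluation (NOSE) scale".
- The same section makes the baseline visit the treatment visit as well: "During the baseline visit, data collection will be performed first", with treatment given afterwards on the same occasion.

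For the analysis, section 4.9 names as outcomes the patient's "ratings of nasal obstruction via a VAS and NOSE score as well as the SNOT-22 questionnaire and peak inspiratory flow rate". It continues: "One-way ANOVA with repeated measures will be used to compare post-treatment vs. baseline measurements and determine the effectiveness of the treatment". The synopsis repeats that sentence. Neither place says which NOSE score counts as baseline.

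**The concern.** A lower cut-off on an imperfectly repeatable score picks out some patients who happen to score high that day. Their next score tends to be lower even if nothing has changed. When the selecting score is also the comparator and there is no control arm, that fall is counted as improvement. It biases one of the two primary symptom outcomes in favour of the device and raises the false-positive rate of its test.

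The cut-off applies to NOSE alone. VAS, SNOT-22 and peak flow go through the same ANOVA and are affected only as far as their fluctuations correlate with those of NOSE.

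Apart from the bias, the schedule needs correcting. A site working from Table 1 would not collect a baseline-visit NOSE score that the text of section 4.7 requires.

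**Working it through.** **Which score does what.** There are three readings.

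1. Table 1 governs. The Screening score is the only pre-treatment NOSE, so it selects and is the comparator.
2. Criterion 6 and the section 4.7 list govern. The baseline-visit score does both.
3. The two are merged. A Screening score admits and a separate baseline-visit score is analysed. No passage states this, the timing word in criterion 6 weighs against it, and section 4.1 counts one pre-treatment session.

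The bias arises in full under readings 1 and 2.

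**Inputs.** From the documents: cut-off 60, up to 20 patients, two time points, no control. With two time points, repeated-measures ANOVA is the paired t-test (F = t²). The documents give no NOSE mean, SD, retest correlation, alpha or power, so there is no figure of the plan's own to reproduce. Assumed: a 0–100 scale in steps of 5, source mean μ 50 to 70, SD σ 15 to 20, retest correlation ρ 0.7 to 0.9, n = 20 with no dropout, two-sided 0.05, no true effect.

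**Same score as selector and baseline.** For normal scores the expected fall is

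(1 − ρ) × σ × λ, with λ = φ(a) / (1 − Φ(a)) and a = (60 − μ)/σ.

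Middle case (μ 60, σ 20, ρ 0.8): a = 0 and λ = 0.399/0.5 = 0.798, so the fall is 0.2 × 20 × 0.798 = 3.19 points. Simulation with scores rounded to 5 and bounded at 0 and 100 gives slightly less. The last column is the share of 20-patient studies with a significant improvement and no true effect (nominal 2.5%).

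| μ / σ / ρ | Pass cut-off | Formula | Simulated fall | False improvement |
|---|---|---|---|---|
| 50 / 15 / 0.7 | 31% | 5.69 | 5.3 | 53% |
| 50 / 20 / 0.7 | 35% | 6.85 | 6.4 | 46% |
| 60 / 20 / 0.8 | 55% | 3.19 | 2.9 | 18% |
| 70 / 20 / 0.7 | 73% | 3.05 | 2.7 | 12–13% |
| 70 / 15 / 0.9 | 80% | 0.64 | 0.6 | 6% |

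**Separate baseline score.** If the Screening score selects and another score is the baseline, the remaining fall is (ρ_SB − ρ_S90) × σ × λ. Here ρ_SB is the Screening–baseline correlation and ρ_S90 the Screening–day 90 correlation. In the middle case:

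- ρ_SB = 0.80: 0 × 20 × 0.798 = 0; simulated 0.0 points, 2.5%.
- ρ_SB = 0.90: 0.10 × 20 × 0.798 = 1.60; simulated 1.4 points, 7%.
- ρ_SB = 0.98 (scores taken nearly together): 0.18 × 20 × 0.798 = 2.87; simulated 2.6 points, 14%.

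Over all the assumed values, ρ_SB halfway between ρ and 1 leaves 0.3 to 3.1 points and 4% to 15%. With ρ_SB = 0.98, 0.4 to 5.9 points and 4% to 45% remain. The separate score gave the smaller bias in every scenario run.

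**Spill-over to VAS.** With NOSE as the selector and VAS given the same retest correlation, the middle case gives a false-improvement rate for VAS of about 2.5%, 5%, 7% or 10% when same-visit fluctuations in VAS and NOSE correlate 0, 0.3, 0.5 or 0.7.

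**The case against.** **The merged reading deserves more weight.** Section 4.7 counts subjects as enrolled when they arrive for the procedure. If eligibility must be settled before that, the qualifying score would be the Screening NOSE, the section 4.7 list would supply a second score, and the only fault would be a missing mark in Table 1. This reading cannot be excluded. It is not decisive either: criterion 6 ties the cut-off to baseline, and section 4.7 also calls the work-up after consent a baseline evaluation, which fits one Screening score serving as baseline.

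**The baseline is implied.** Sections 4.1 and 4.7 do point to the pre-treatment visit, where "During the baseline visit, data collection will be performed first". But nothing settles the matter for NOSE, the one outcome Table 1 leaves out of that visit.

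**The size rests on assumptions.** This stands. The highest rates need a source mean of 50, where only 31% to 35% of candidates would pass. Candidates must also have at least a year of complaints, failed medical therapy and nasal valve involvement, which may make the cut-off bind less. At a source mean of 70 the effect is 0.6 to 2.7 points and 6% to 13%. The direction of the bias does not depend on these values.

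**The remedy is partial.** This also stands. Scores taken close together leave most of the bias, and an uncontrolled series of up to 20 patients keeps its main limits whatever is done here.

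**Conclusion.** The concern holds and should be fixed. The scheduling contradiction is certain, and so is the absence of a named NOSE baseline. On either single-score reading the selecting score is the comparator, and the bias favours the device.

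The size is not known. Under the stated assumptions it ranges from slight to a false-improvement rate of about one half, with a middle case of 2.9 points and 18% against a nominal 2.5%. This does not show that regression to the mean would explain a large fall in NOSE. Confidence is medium, because the merged reading would remove some or all of the bias and no passage rules it out.

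**What to change.** Reconcile criterion 6 (synopsis and section 4.3), Table 1 and the section 4.7 list, as follows.

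1. Criterion 6, both places: apply the cut-off of 60 to the Screening NOSE only.
2. Table 1: add a mark for NOSE under Baseline/Study Procedure. In the section 4.7 list, state that this NOSE is completed before treatment and on a later day than the Screening NOSE, that no cut-off applies to it, and that both dates are recorded.
3. Section 4.9 and the synopsis: state that the NOSE baseline is the score from the Baseline/Study Procedure visit, not the Screening score used for eligibility.
4. In the same two places, replace the claim to determine effectiveness with an aim to estimate the change from baseline. Add that, without a control group, this change may include regression to the mean, placebo response and natural course.

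The separate score removes regression to the mean only if the Screening–baseline and Screening–day 90 correlations are equal. Otherwise it reduces it, and little is gained if the two scores are taken almost together.

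**Cost.** One short questionnaire, already listed for an existing visit, plus wording. A site that would screen and treat on one day must collect the Screening NOSE on an earlier day. The baseline mean, and with it the reported improvement, will be lower: in the middle case 71.2 to 72.7 instead of 74.2 (ρ_SB 0.8 to 0.9). Some treated patients will have a baseline below 60: 13% to 18% in that case, or 0.13 × 20 = 2.6 to 0.18 × 20 = 3.6, about 3 to 4 of 20.
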